**Inclusion Criteria:**

1. 18-68 years of age
2. SCI  $>1$  year in duration
3. Level of SCI C4-T2, AIS A & B
4. Gender and age-matched ( $\pm 5$  years) AB controls
5. Euhydration (participants will be instructed to avoid caffeine and alcohol, maintain normal salt and water intake and avoid strenuous exercise for 24 hours prior to study).

**Exclusion Criteria:**

1. known cardiovascular, kidney or untreated thyroid disease
2. traumatic brain injury (mod-severe)
3. diabetes mellitus
4. acute illness or infection
5. broken, inflamed, or otherwise fragile skin
6. pregnancy
7. BMI  $>30 \text{ kg/m}^2$
8. smoking

**Methods:** On 3 separate days (Phases 1 & 2), participants will arrive in the laboratory between 8:00-11:00 AM.

**Preparation for Study Visits:** Participants will be instructed to avoid caffeine and alcohol, maintain normal salt and water intake, and avoid strenuous exercise for 24 hours prior to study on each visit. Participants will wear a T-shirt and shorts during all visits to maximize skin exposure to the warm temperature. The T-shirt will also prevent the cooling vest from directly touching the skin. Each participant will be instructed to eat a light meal (plain bagel or 2 pieces of toast) 2 hours prior to their visit. Participants will be asked to empty their bladders prior to the study visit and again upon arrival, if necessary.

**Instrumentation:** (*For all participants*) After obtaining informed consent, participants will be instrumented in a thermoneutral room ( $25^{\circ}\text{C}$ ) and in their wheelchair (Hi-SCI) or a provided wheelchair for AB controls. Participants will remain seated and relatively still but will be instructed to use their pressure relief seat cushion (e.g., Roho) and maintain their usual pressure relief schedule (e.g., weight shifting every 15 minutes). Laser Doppler flowmetry (LDF) will be used to measure changes in microvascular perfusion rate by placing a Doppler probe on the skin of the ventral forearm and calf bilaterally as an index of vascular sympathetic withdrawal. Changes in skin blood flow will be assessed from calculations of cutaneous vascular conductance (CVC = LDF/MAP), a more accurate measure of change in skin blood flow. An automated blood pressure cuff will be placed above the elbow to measure brachial blood pressure (BP) and heart rate (HR). Sweat rate (SR) will be measured by the Quantitative Sweat Measurement System (WR Medical Electronics, Stillwater, MN) with capsules secured to 4 sites: left

upper arm, left forearm, left mid-thigh, and left midcalf (C5, T1, L3, and L5 dermatomes, respectively). A pulse oximeter will be placed on the second digit to detect blood oxygen saturation. An infrared ear thermometer will be used to assess tympanic temperature.

**For AB participants (Visit 1):** Skin thermocouples will be secured at 12 sites on the ventral and dorsal torso (mid-clavicular line from T3 to T10 dermatomes, bilaterally) for collection of skin temperatures (Tsk).

**For participants with Hi-SCI (Visits 2 & 3):** Participants with Hi-SCI will be asked to empty their bladders to minimize risk of AD during the heat stress protocols (*wet vest, no vest*). Skin thermocouples will be secured at 14 sites, 10 skin thermocouples on the ventral and dorsal torso (five on each side) and 4 additional thermocouples on both hands and feet (2 on each side) for distal skin temperatures as an indirect index of sympathetic vasomotor regulation. A disposable forehead skin temperature sensor (Bair Hugger™ Spot On™ Temperature Monitoring System, 3M, Maplewood, Minnesota) will be placed on the orbital bone, above the eyebrow, on whatever side is most comfortable for the participant in order to measure core temperature (Tcore).

**Baseline Collection (BL):** (for all 3 Visits) At the end of the instrumentation period (~30 minutes) at 25°C while seated and wearing only shorts and a standard T-shirt, a baseline (BL) collection of the following parameters will be performed for 15 minutes. Tcore (in persons with Hi-SCI only) and Tsk will be measured continuously. Subjective ratings of thermal sensation, assessed on a 9-point scale (TS) and general thermal comfort on a 6-point scale (TC). HR, BP, blood oxygen saturation, tympanic temperature and 5 minutes of LDF will be measured at 10-minute intervals. BP will be assessed immediately pre and post each LDF interval for calculation of CVC. SR will be measured for 15 minutes continuously.

**1. Thermal Challenge for Safety and Comfort Study (Phase 1; 1 visit, AB participants only):** AB participants will be fitted with an appropriately sized cooling vest while seated in a wheelchair at the end of BL. Participants will be transferred into a pre-heated (35°C, 35% relative humidity) thermal chamber for 2 hours with the wet cooling vest on full power. Skin temperatures will be continuously measured at multiple sites under the vest. TC and TS will be assessed every 10 minutes. Participants will be queried if they feel any areas of cold-related discomfort or numbness (cold spots), or any other feelings of discomfort from the vest. LDF will be measured as above, but at 20-minute intervals. SR will be measured for 15 minutes every 30 minutes (4 times). HR, BP, blood oxygen saturation and tympanic temperature will be assessed at 10-minute intervals. **Determinants of success for Phase 1:** 1) Skin thermocouple temperatures maintained  $\geq 20$  °C, and 2) subjective ratings of TS not less than “cool” (i.e., not “cold” or “very cold”) on the 9-point TS scale.

**2. Thermal Challenge with Wet Cooling Vest vs. No Vest (Phase 2; 2 visits, participants with Hi-SCI only):** After 15 minutes of baseline data collection in a thermoneutral environment (25°C), participants with HI-SCI will be fitted with an appropriately sized cooling *wet vest* or will wear *no vest* (in random order). To provide evaporative heat loss, the vest material will be saturated with water using a spray bottle. Participants will then be transferred into a warm (35°C, 35% relative humidity) thermal chamber for up to 2 hours. Tcore (Bair Hugger™ Spot On™ forehead skin sensor ) and Tsk (thermocouples at multiple sites under the vest and on hands and feet) will be measured continuously; subjective TS and TC will be measured at 10-minute intervals; LDF will be measured as above (for CVC) at 20-minute intervals. SR will be measured for 15 minutes every 30 minutes (4 times). HR, BP, blood oxygen saturation, and tympanic temperature will be measured at 10-minute intervals for vital signs' information. Participants will be queried if they have any feelings of discomfort. If the participant's Tsk underneath the vest falls below 20°C, or Tcore rises to 38°C, and/or the participant requests study termination because of discomfort, the vest will be removed, the heat challenge will be immediately terminated, and the participant will be transferred to a cool environment, covered with cool blankets, as appropriate, and provided cold liquids. The study physician will be directly responsible for subjects' medical safety during study protocols. Subjects' Tcore, HR and BP, will be monitored at frequent intervals. Symptoms suggestive of AD or hyperthermia will be assessed every 10 minutes. The study physician will be notified immediately of any symptoms or signs of concern. Subjects will be medically evaluated promptly, and the study terminated if any safety issues arise. Subjects will be monitored for at least 30 minutes of recovery to ensure Tcore returns to within 1% of BL value.

**Determinants of Efficacy Failure or Success for Phase 2:** 65% of participants in the *wet vest* condition will have a significantly reduced elevation in Tcore ( $\leq 0.3^{\circ}\text{C}$ ), and 2) a greater percentage will report increased thermal comfort (decreased perception of feeling “hot”, “very hot”, or “uncomfortable”) compared to the expected increase in Tcore of  $0.6^{\circ}\text{C}$  and reported thermal comfort in the *no vest* condition.

**Outcome Variables:** **Phase 1:** Skin thermocouple temperatures, ratings of thermal comfort and sensation, cold spots, and any reported physical discomfort from the vest. **Phase 2:** The primary endpoint will be the magnitude and rapidity of the rise in Tcore upon exposure to a warm environment. The perception of thermal comfort and sensation of heat will be obtained as secondary endpoints.

**Procedures: Thermoregulatory Measurement Procedures:** The following measurements will be

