**Secondary Objective (Efficacy in SCI):** To determine the efficacy of the wet cooling vest to maintain Tcore (within 0.3°C) in participants with Hi-SCI when exposed to 2 hours of a warm environment. Using a repeated measures design, participants with Hi-SCI will wear the wet vest (experimental condition) or no vest (control condition) in a warm thermal chamber (35°C) for up to 2 hours in the seated position, to determine: (1) change in Tcore and (2) perception of heat and thermal comfort.

**Secondary Hypotheses:** In our previous investigation of heat exposure, 65% of persons with Hi-SCI had increases of  $> 0.5^\circ\text{C}$  in Tcore (mean increase  $0.6 \pm 0.3^\circ\text{C}$ ) while wearing only shorts. We expect that

wearing a cooling vest during the same heat exposure, will significantly increase heat dissipation and, thus, enhance maintenance of Tcore and thermal comfort. We hypothesize that during a controlled warm exposure (35°C), participants with Hi-SCI wearing the wet cooling vest compared to the same participants not wearing a vest: 1) 65% will have a significantly reduced elevation in Tcore ( $\leq 0.3^{\circ}\text{C}$ ), and 2) a greater percentage of participants will report increased thermal comfort (decreased perception of feeling “hot”, “very hot”, or “uncomfortable”).

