## **3. PROCEDURES, METHODS AND EXPERIMENTAL DESIGN.**

**Research Design:** An exploratory protocol with two phases (AB safety; SCI safety and efficacy) will be performed. In Phase 1, because those with Hi-SCI potentially have impaired or absent skin temperature sensation, AB participants will wear the wet “smart” cooling vest to determine its safety. Phase 2 will be performed for efficacy in a single group of persons with Hi-SCI in a prospective, repeated measures design with two conditions (experimental: *wet vest*, control: *no vest*) administered in random order. The objective of Phase 2 is to determine if persons with Hi-SCI dissipate body heat more effectively in the *wet vest* condition compared to the *no vest* condition as evidenced by a smaller rise in Tcore, a decreased perception of heat, and increased thermal comfort. We expect a mean increase in Tcore of  $0.6 \pm 0.3^{\circ}\text{C}$  and a perception of feeling “hot or very hot” in the *no vest* condition, as evidenced in two of our prior studies with identical challenges.

**Participants:** Ten participants with high-level SCI (C4-T2, AIS A & B) and 5 AB participants matched for age ( $\pm 5$  years) and gender will be recruited for study participation.

**Participant Recruitment:** Patients referred by their physician following routine physical examinations will be approached for potential study enrollment. Physicians will be informed of the inclusion and exclusion criteria and will be able to assure us that the patient is an appropriate study participant and that he/she is willing to speak with the study coordinators.

1. Veterans with SCI responding to IRB-approved articles in lay publications and advertisements.
2. Veterans with an ongoing relationship with our center (Metabolic, Pulmonary, or GI SCI clinics).

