**Sample Size and Statistical Approach:** We are hypothesizing that after 2 hours of heat exposure, the average increase in Tcore of persons with Hi-SCI with the wet cooling vest will be  $0.3 \pm 0.3^{\circ}\text{C}$  compared to an increase of  $0.6 \pm 0.3^{\circ}\text{C}$  (data from our prior study using an identical heat challenge, but with no vest). Therefore, a sample size of 10 participants would be needed to achieve a power of 81% for a two-sided, one-sample analysis at an alpha of 0.05. For Phase I (safety), descriptive statistics will be used to determine the number of participants who have a vest failure. Vest failure will be defined as any area of skin under the vest (Tsk) with a temperature  $<20^{\circ}\text{C}$  and/or the number of participants who report a TS of “cold” or “very cold”. For efficacy testing, a 2 x 2 (condition, time) repeated measures ANOVA will be used to determine significant main or interaction effects. If main or interaction effects are determined, post hoc analysis will be performed using t-tests or appropriate non-parametric tests to determine significant differences between conditions. Significance will be set at an alpha level of 0.05.

3a. Basic Information - Even if described under “Procedures”, list the following information, where pertinent:

3a. i) Procedures to be used (e.g., biopsy, surgical operation, interview, experimental diet, infusion, drug administration, etc.) and with what frequency?

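### The Phase 2 success rule (65% of vest wearers with a Tcore rise of at most 0.3°C) does not fit the planned mean vest rise of 0.3°C, at which only about half are expected to qualify

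*Combined protocol and SAP*

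**What the plan says.** Section 3, under the determinants of efficacy failure or success for Phase 2, requires that "65% of participants in the *wet vest* condition will have a significantly reduced elevation in Tcore", followed in brackets by a rise of at most 0.3°C. A greater percentage must also report better thermal comfort. The secondary hypotheses in Section 1 contain the same Tcore statement: "65% will have a significantly reduced elevation in Tcore".

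The sample size paragraph of Section 3 works from a mean. It assumes that "the average increase in Tcore of persons with Hi-SCI with the wet cooling vest will be" 0.3 ± 0.3°C, against 0.6 ± 0.3°C without a vest, and states that 10 participants give "a power of 81% for a two-sided, one-sample analysis at an alpha of 0.05". For the analysis, a 2 x 2 (condition, time) "repeated measures ANOVA will be used to determine significant main or interaction effects". The outcome variables paragraph names a continuous endpoint: "The primary endpoint will be the magnitude and rapidity of the rise in Tcore upon exposure to a warm environment".

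The documents do not derive the 65%. The same figure appears twice as a description of the earlier no-vest cohort. Section 1 reports that "65% of persons with Hi-SCI had increases of" more than 0.5°C. Section 4 reports that 13 of 20 had greater sympathetic interruption.

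**The concern.** The cut-off applied to each participant is the same number as the mean the vest is planned to achieve. In a roughly symmetric distribution half the values lie at or below the mean, whatever the SD, so a 65% pass mark asks for a better vest than the one the trial is sized for.

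Three further gaps make the rule hard to apply:

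- No passing count is given, and 65% of 10 is not a whole number.
- A significant reduction is not defined for one person with one visit per condition. The bracketed limit may be the intended definition, but the text does not say so.
- A continuous endpoint, a test of its mean and a responder share can coexist, but nothing says which stands when they disagree.

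At stake is the Phase 2 conclusion. The trial could show a clear mean reduction and still be declared an efficacy failure. Section 5 makes a follow-on application conditional on efficacy. It describes efficacy as keeping Tcore within 0.3°C and does not cite the 65%, so the link from this rule to that decision is inferred.

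**Working it through.** **Inputs.** From the sample size paragraph: vest rise 0.3 ± 0.3°C, no-vest rise 0.6 ± 0.3°C, n = 10, two-sided alpha 0.05. From the Phase 2 determinants: cut-off 0.3°C, pass mark 65%.

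**The plan's own power.** Effect size = (0.6 − 0.3)/0.3 = 1.0. A two-sided one-sample t-test with 9 degrees of freedom and noncentrality 1.0 × √10 = 3.16 has power 80.3%. The plan states 81%, so the figure reproduces to within a point and the 0.3 is being used as an SD.

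**Expected responder share.** With normal rises, P(rise ≤ 0.3) = Φ((0.3 − 0.3)/0.3) = Φ(0) = 50%. For an expected 65% at SD 0.3, the mean rise would have to be 0.3 − 0.3 × 0.385 = 0.18°C.

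**Chance of passing.** 0.65 × 10 = 6.5. Six of 10 is 60% and falls short, so 7 are needed. For a Binomial(10, 0.5), P(≥7) = (120 + 45 + 10 + 1)/1024 = 176/1024 = 17.2%, so failure is 82.8%. If the comfort criterion must hold as well, 17.2% is an upper limit.

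**Sensitivity.** All rows have mean 0.3 and SD 0.3. The shapes are assumptions and do not bound the answer.

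| Assumption | Responder share | Fails, 7 of 10 needed | Fails, 6 of 10 accepted |
|---|---|---|---|
| Two-subgroup shape from Section 4, rescaled | 48% | 85% | 66% |
| Normal | 50% | 83% | 62% |
| Normal, rises rounded to 0.1°C (cut-off effectively 0.35) | 57% | 70% | 45% |
| Exponential | 63% | 53% | 29% |
| Lognormal | 66% | 46% | 22% |

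Even if the true share were exactly 65%, 7 of 10 would be missed 49% of the time.

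**Agreement with the mean comparison.** This was simulated with normal rises, SD 0.3 in both conditions and 7 of 10 needed. For the one-sample test against 0.6°C, 63% of trials are significant but fail the rule, 17% are significant and pass, and 20% are non-significant and fail. Under the exponential shape, 33% are significant but fail and 42% are significant and pass.

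For a paired test, the between-visit correlation is not in the documents, so a range is shown:

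| Assumed correlation | Power, n = 10 | Significant but rule failed | Rule failed, given significant |
|---|---|---|---|
| 0 | 51% | 37% | 72% |
| 0.3 | 66% | 51% | 77% |
| 0.5 | 80% | 64% | 80% |
| 0.7 | 95% | 78% | 82% |

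**Alternative pass marks.** With normal rises, the no-vest responder share is Φ((0.3 − 0.6)/0.3) = 16%.

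| At least this many of 10 | Passes at the planned vest rise | Passes at the no-vest rise |
|---|---|---|
| 4 | 83% | 6% |
| 5 | 62% | 1% |
| 6 | 38% | 0.2% |
| 7 | 17% | 0.02% |

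The no-vest column is sensitive to shape. With the Section 4 subgroups as printed (65% at 0.8 ± 0.3°C, 35% at 0.3 ± 0.3°C), the no-vest share is 20.6%, and at least 4 or 5 of 10 pass 13% or 3.7% of the time. Those subgroups imply an overall SD of 0.38 rather than 0.3, so this is a sensitivity and not a correction.

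**The case against.** The arithmetic is not in dispute; the objections concern emphasis, precedence and remedy.

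- The 83% needs both normal rises and a 7-of-10 reading, and the plan states neither. Other assumptions give much lower failure rates. This stands: the firm result is that the cut-off equals the planned mean, and the 83% is conditional.
- The heading over the rule suggests that it decides efficacy and that the ANOVA only supplies the inference. This is a plausible reading, but it is not stated, and under it the deciding rule is the one whose operating characteristics were never worked out.
- The share of significant trials that fail the rule is close to the unconditional 83%, so it is largely the same fact seen from the other side. That is fair. It shows how often two verdicts would conflict and is not a second defect.
- The secondary objective in Section 1 is to hold Tcore within 0.3°C. That can be read as a goal for each individual, which a significant mean reduction would not establish. This is the strongest point, and it makes keeping a repaired responder rule a legitimate choice.
- A go/no-go rule may properly be stricter than a test of the mean. It may, but its chance of passing should then be stated.
- The trial is an exploratory pilot with safety as its primary objective, and continuous Tcore is collected in both conditions, so any summary can be computed later. This limits the consequence. It does not settle the rule by which success will be declared.

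**Conclusion.** The concern holds. As written, the pass mark is inconsistent with the planning assumption: about 50% of participants are expected to meet the cut-off, given only rough symmetry. With normal rises and 7 of 10 needed, a vest that performs as planned fails the Tcore part 83% of the time. The size depends on distribution and count; failure ranges from 22% to 85% over the cases tried, and those cases are not limits. The 81% power is not in error, but it does not describe this rule.

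This should be fixed, at modest severity: efficacy is a secondary objective, and safety and data collection are unaffected. Confidence is high in the mismatch and conditional for the 83%.

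**What to change.** Reconcile the secondary hypotheses in Section 1 with the Phase 2 determinants, outcome variables and sample size paragraphs in Section 3. Either of two routes would do.

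1. Preferred: decide Phase 2 Tcore efficacy on the mean rise, as the within-participant vest minus no-vest difference with its 95% CI. This fits the Research Design paragraph, which looks for better heat dissipation with the vest than without, "as evidenced by a smaller rise in Tcore, a decreased perception of heat, and increased thermal comfort", and the planned repeated measures analysis. Report the share with a rise of at most 0.3°C descriptively in both conditions with exact CIs; 5 of 10, for example, has a 95% CI of 19% to 81%.
2. If the responder rule is kept because individual protection is the aim: state the passing count out of 10, a pass mark or assumed vest effect consistent with the sample size paragraph, the chance of passing with and without a vest effect, and which verdict stands if it disagrees with the mean comparison.

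In both cases, drop the word for statistical significance where it is applied to single participants.

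The cost is rewording, with no new data, visits or participants. There are two downsides. The stated responder expectation becomes less favourable, about 50% instead of 65%. The power of a paired comparison at n = 10 also rests on a between-visit correlation that the documents do not give, and runs from 51% at correlation 0 to 95% at 0.7.

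### The comfort half of the Phase 2 success rule can be met by one participant in ten; a vest with no effect on comfort would meet that half by chance roughly 14–41% of the time under assumed inputs

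*Combined protocol and SAP*

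**What the plan says.** The paragraph on determinants of efficacy failure or success for Phase 2 (Section 3) sets two conditions, both required. The first is on core temperature: "65% of participants in the" wet vest condition are to have a rise of 0.3°C or less. The second is on comfort: "a greater percentage will report increased thermal comfort", judged against the no-vest condition. The Secondary Hypotheses in Section 1 say the same: "a greater percentage of participants will report increased thermal comfort".

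The design is within-person: "Phase 2 will be performed for efficacy in a single group of persons with Hi-SCI in a prospective, repeated measures design with two conditions", given in random order to ten participants. Outcome Variables (Section 3) lists comfort and heat sensation as secondary endpoints. Table 1 schedules 12 ratings on each of two scales during the heat exposure: thermal sensation (9 points) and thermal comfort (6 points).

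Under Sample Size and Statistical Approach the efficacy analysis is described as follows: "a 2 x 2 (condition, time) repeated measures ANOVA will be used". T-tests or non-parametric tests follow only if that model shows an effect. The section adds: "Significance will be set at an alpha level of 0.05".

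**The concern.** A criterion that asks only for a larger percentage is met by the smallest difference the data can show. With ten people that is one person, and one person changing category between two visits is ordinary variation. The rule compares two overall percentages although every participant supplies both responses. It does not say which scale or which of the 12 ratings counts.

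The analysis section does not close the gap. It names no test for a paired percentage, makes the non-parametric step conditional on the ANOVA, and never says that the comfort criterion needs a significant result.

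At stake is the comfort conclusion. It is a hypothesis in its own right and, under Significance of Current Research (Section 5), part of the efficacy goal that precedes a full grant application.

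**Working it through.** **The plan's own figure.** The only power stated is for core temperature: "a sample size of 10 participants would be needed to achieve a power of 81% for a two-sided, one-sample analysis at an alpha of 0.05". The inputs are mean rises of 0.3 and 0.6°C, SD 0.3, so d = (0.6 − 0.3)/0.3 = 1.0. A one-sample t-test with n = 10 and noncentrality √10 = 3.16 has power 80.3%, which agrees with 81% to within rounding of method. No error rate or power is given for comfort.

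**Inputs for the comfort criterion**
- n = 10, paired (Section 3).
- Pass if more participants do better with the vest than do worse; this is the same as a larger percentage with the vest.
- p, the proportion feeling hot without the vest: not given. The earlier tetraplegia study (Section 4) is described only in words. Assumed 0.5–0.9.
- φ, the correlation between a participant's two yes/no responses: not given. Assumed 0–0.8.
- One yes/no response per visit, because the rule fixes neither scale nor time point.

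**Formula.** If the vest has no effect on comfort, a participant's two responses differ with probability q = 2p(1 − p)(1 − φ), and each difference is equally likely to favour either condition. By symmetry

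P(pass) = [1 − P(tie)]/2, where P(tie) = Σₖ C(10, 2k) q²ᵏ (1 − q)¹⁰⁻²ᵏ C(2k, k)/4ᵏ.

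**Worked case, p = 0.9 and φ = 0.8.** q = 2 × 0.9 × 0.1 × 0.2 = 0.036. The first three terms of P(tie) are 0.6931 + 0.0217 + 0.0001 = 0.715, so P(pass) = 0.285/2 = 14%.

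| p | φ = 0 | φ = 0.5 | φ = 0.8 |
|---|---|---|---|
| 0.5 | 41.2% | 37.2% | 27.5% |
| 0.8 | 38.8% | 33.2% | 21.4% |
| 0.9 | 34.4% | 26.1% | 14.3% |

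The 41% is a ceiling for independent or positively correlated responses. The 14% is the lowest value in this grid, not an absolute floor: p above 0.9 or φ above 0.8 lowers it further. For small q, P(pass) is about 10q/2 = 5q. It falls to the 2.5% that a two-sided 0.05 test allows for favourable false claims only when q is about 0.005, that is, when only about one person in 200 would change category.

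**The core temperature half.** With ten people, 65% means at least 7. If the vest leaves rises at mean 0.6, SD 0.3 and normal, P(rise ≤ 0.3) = Φ(−1) = 15.9%, and P(7 or more of 10) = 0.02%. Using instead the two subgroups of the earlier Hi-SCI study in Section 4 (65% with 0.8 ± 0.3, 35% with 0.3 ± 0.3), the chance per person is 0.65 × Φ(−0.5/0.3) + 0.35 × 0.5 = 20.6%, and P(7 or more) = 0.1%. The joint rule cannot pass more often than this half alone.

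**The case against.** **The whole rule is protected.** A reader might infer that an ineffective vest would be declared a success in up to 41% of trials. The documents do not support that. Both halves are required, and a vest with no effect on core temperature passes that half about 0.02–0.1% of the time. This objection stands and limits the point to the comfort claim. It gives no protection when the vest does limit core temperature but does not improve comfort.

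**An analysis and an alpha are stated.** It would also be too strong to say that comfort has no error control at all. The ANOVA is within-person, is introduced for efficacy testing in general, and could be read as covering both rating scales at 0.05. What remains is that the success rule does not refer to it.

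**The figures rest on assumptions.** This also stands. It is tempting to quote only the 34–41% for independent visits. But this is a repeated measures design in which participants are expected to feel hot or very hot without the vest, so a high p and a positive correlation are plausible, and both lower the figure. Even so, 14% is more than five times 2.5%.

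**This is an exploratory pilot and comfort is secondary.** That is a fair reason to report comfort descriptively. It is a weaker reason to make success or failure turn on an unqualified difference in percentages.

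**Conclusion.** The concern holds in a limited form. As written, the comfort criterion is a decision rule that one participant in ten can satisfy, and it is not linked to the ANOVA or to the 0.05 level. For a vest with no effect on comfort it is met by chance about 14–41% of the time, given 50–90% feeling hot without the vest, a response correlation of 0–0.8, and a single yes/no response per visit. The freedom to choose among two scales and 12 ratings is not counted in that range. The consequence is a false comfort claim, not a false declaration on the full Phase 2 rule. The change should be made; because comfort is a secondary endpoint in a pilot, it does not undermine the core temperature comparison.

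**What to change.** - Name one scale as the comfort criterion, for example the 6-point thermal comfort scale, with the 9-point thermal sensation scale as supportive. Testing both at 0.05 without choosing would reopen the error-rate problem.
- For each participant take the rating at the last time point reached in both visits.
- Test the within-person difference with an exact Wilcoxon signed-rank test at two-sided 0.05, not conditional on a significant ANOVA. This holds favourable false claims at or below 2.5%.
- Report how many improved, were unchanged and were worse, with a confidence interval. Keep the percentages as description.

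Keeping the ordinal rating is preferable to testing hot versus not hot. An exact two-sided McNemar test needs at least six participants who change, all in favour if there are exactly six (2 × 0.5⁶ = 0.031; five out of five gives 0.0625).

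The cost is a change of wording and one simple test on ratings already scheduled. The criterion becomes harder to meet. For an assumed one-point benefit on the 9-point scale (SD 1 per visit, correlation 0.5), simulated power is about 57–60%, and lower if no-vest ratings crowd the top of the scale. Power on the 6-point scale was not computed, and the documents give no SD for it. A non-significant result should therefore not be read as evidence of no benefit.
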